#### Statistical Analysis Plan

Statistical analyses were conducted using an intent-to-treat approach. Descriptive statistics were used to summarize continuous outcomes and covariates by experimental condition; frequencies and percentages were used to summarize categorical measures. Given the varying sizes of SSPs, counts of naloxone doses and individuals receiving naloxone were summarized as a rate per number of participant contacts for syringe services in the past 3 months.

Negative binomial regression models were used to compare the number of naloxone doses distributed and contacts for naloxone refills or trainings by condition; the number of contacts for syringe services in the past 3 months was included as an offset. The model for naloxone doses was adjusted for baseline rate given the difference between conditions at baseline. The mean number of best practices adopted were compared by condition using a two-sample t-test. We also carried out a per-protocol dose response analyses, where OMIE SSPs were dichotomized at the median for the number of OMIE sessions (<10 sessions; 10+ sessions) and number of OMIE hours received (<12 hours; 12+ hours) and compared to Control SSPs. P-values <0.05 were considered statistically significant a priori. All analyses were conducted using Stata 16.1 (StataCorp LLC, Texas USA).

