## **Scientific Background**

The United States (US) continues to face decades-long increases in opioid overdose mortality [1]. The Centers for Disease Control and Prevention (CDC) estimates nearly 775,000 people have died of an opioid overdose since 1999 [2]. Between 2020 and 2021, overdose mortality rates involving heroin and synthetic opioids, other than methadone, increased 22%. Overall, drug overdose deaths in the US increased for all genders; all age groups over the age of 25; American Indian/Alaskan Native, non-Hispanic White, non-Hispanic Black, Hispanic, and Native Hawaiian/Pacific Islander communities; all census regions; and urban, suburban, and rural settings [3].

Opioid overdoses involve a toxic dose of natural opioids like heroin, semi-synthetic opioids like oxycodone, and/or synthetic opioids like fentanyl. Naloxone, an opioid antagonist, is an evidence-based biomedical intervention that effectively reverses opioid overdose when administered intranasally or intramuscularly [4-7]. Opioid antagonists bind to the brain's opioid receptor sites, which displaces any opioid currently in the system and temporarily negates their effects, saving the individual's life. Use of naloxone does not cause dependence or tolerance, and can, though not always, precipitate withdrawal [5-8]. Naloxone can dramatically reduce opioid overdose mortality when distributed to people likely to experience or witness an opioid overdose and packaged with education on its use, known as overdose education and naloxone distribution (OEND)[9-14].

Syringe services programs (SSPs) have a primary function of distributing safe drug use supplies, such as sterile syringes, pipes, injection-related equipment, wound care materials, etc., to facilitate the reduction of harms associated with drug use for their participants. Often, SSPs are the first to hear from their participants regarding changes in the unregulated drug market, drug use trends, and overdose experiences. Most SSPs provide a variety of other evidence-based interventions to improve the health of people who use drugs, including OEND [15-18]. SSPs reach people at high risk for experiencing or witnessing an opioid overdose, and pioneered the development of OEND [19-21]. With staff who are culturally competent in providing services for people who use opioids and pre-existing delivery systems designed to reach participants in their own environment, SSPs are an ideal venue for OEND.

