#### Trial Outcomes

Our primary outcomes center on the multidimensional variable of implementation effectiveness (i.e., the consistency and quality of OEND implementation by SSP staff). Implementation effectiveness fit our broad objectives, by focusing on the extent to which our multifaceted, facilitation-based approach impacted OEND delivery at the organizational level. Accordingly, SSPs represent the primary unit of analysis. Proctor et al.'s taxonomy of implementation outcomes informs our operationalization of implementation effectiveness, focusing on the reach of SSPs' naloxone distribution (i.e., consistency) and fidelity to OEND best practices (i.e., quality)[46]. As such, the primary outcomes were the number of naloxone doses distributed in the past 3 months; the number of SSP participants receiving naloxone in the past 3 months, and the number of OEND best practices implemented. Importantly, prior research has shown that larger scale naloxone distribution has led to reductions in opioid overdose mortality, further supporting use of these measures as trial outcomes [17, 47, 48].

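### A primary outcome is declared as a count of people receiving naloxone, but the model as worded analyses refill or training contacts; the two sections need to be reconciled

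*Combined protocol and SAP*

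**What the plan says.** The Trial Outcomes section names three primary outcomes: naloxone doses distributed, "the number of SSP participants receiving naloxone in the past 3 months", and the number of best practices implemented. It links them to reach and fidelity, describing "our operationalization of implementation effectiveness, focusing on the reach of SSPs" (the sentence goes on to their naloxone distribution and to fidelity to best practices).

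The Statistical Analysis Plan refers to the second outcome in two ways. In the descriptive paragraph, "counts of naloxone doses and individuals receiving naloxone were summarized as a rate per number of participant contacts". In the next paragraph, negative binomial models are used to compare "the number of naloxone doses distributed and contacts for naloxone refills or trainings by condition", and "the number of contacts for syringe services in the past 3 months was included as an offset". The third outcome has its own sentence: "The mean number of best practices adopted were compared by condition using a two-sample t-test".

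Refill or training contacts appear nowhere else. The Trial Outcomes section does not list them as an outcome, the Covariates section does not list them as a baseline measure, and no section defines them or says that they are the same as participants receiving naloxone.

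**The concern.** Persons and contacts are different units. Read literally, someone who is trained and later returns for a refill within the 3 months is one participant but two contacts. The Statistical Analysis Plan itself uses both words in one sentence, with individuals in the numerator and syringe-service contacts in the denominator, so a reader has reason to think that they are not interchangeable.

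What is at stake is the meaning of the reach result. Reach, as the Trial Outcomes section sets it up, concerns how many participants are supplied. A contact count can rise because the same people return more often, with no further person reached, and it can stay flat while more people are each seen once. If the model is run as worded and reported as the declared outcome, a difference in return visits could be read as a difference in people reached, or could hide one.

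**Working it through.** **Step 1: match each declared outcome to its analysis.**

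| Primary outcome (Trial Outcomes) | Descriptive summary (Statistical Analysis Plan) | Between-arm analysis (Statistical Analysis Plan) |
|---|---|---|
| Naloxone doses distributed | Doses per syringe-service contact | Negative binomial on doses, offset syringe-service contacts, adjusted for baseline rate |
| Participants receiving naloxone | Individuals per syringe-service contact | Negative binomial on refill or training contacts, offset syringe-service contacts |
| Best practices implemented | Not separately specified | Two-sample t-test on best practices adopted |

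The unit changes only in the second row, from persons (outcome and summary) to contacts (model).

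**Step 2: how the two ratios relate.** The plan gives no figure on this point to reproduce; the sample size calculation uses a standardised effect and refers to neither unit. For each arm let P be participants receiving naloxone, C refill or training contacts, and S syringe-service contacts. Then

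C/S = (P/S) × (C/P).

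Dividing the OMIE arm by the Control arm:

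contact rate ratio = participant rate ratio × (C/P in OMIE ÷ C/P in Control).

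The offset S is the same in both versions, so it does not alter the last factor. The ratios agree only if that factor is 1, that is, if contacts per participant are equal between arms. The identity concerns the underlying arm-level rates; fitted estimates would follow it approximately.

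**Step 3: an illustration.** The documents give no contacts-per-participant figure, so the inputs here are assumptions. Suppose that each participant has at most one further contact in the 3 months. Then C/P = 1 + the share with a further contact.

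- 50% in OMIE, 25% in Control: 1.50 ÷ 1.25 = 1.20. A true participant ratio of 1.00 appears as 1.00 × 1.20 = 1.20.
- 25% in OMIE, 50% in Control: 1.25 ÷ 1.50 = 0.83. A true participant ratio of 1.00 appears as 1.00 × 0.83 = 0.83.
- Equal shares: the factor is 1 and there is no distortion.

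The direction is not known in advance, because nothing in the documents says which arm would have more repeat contacts.

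**The case against.** The strongest reply is that this is one survey item under two names. The structure of the Statistical Analysis Plan supports that. Its first paragraph pairs doses with individuals over syringe-service contacts; its second pairs doses with refill or training contacts, with syringe-service contacts as the offset. Position, partner variable and denominator are all the same. Naming is loose elsewhere too: best practices are implemented in one section and adopted in another, and the wording for the size variable varies between the Covariates section and the Statistical Analysis Plan. The Scientific Background describes naloxone as effective "when distributed to people likely to experience or witness an opioid overdose and packaged with education on its use". If training goes with first supply and refills are repeat supply, then refills or trainings together cover every occasion of receiving naloxone, as a second label for recipients might.

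Much of this stands. A reader might infer from the mismatch that one of the three primary outcomes has no test. The documents do not support that: they neither equate the two terms nor show that two variables were collected, and the parallel structure makes a single item plausible. It also stands that the illustration rests wholly on assumed inputs, and that no figure in the documents suggests that contacts per participant differ between arms.

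The reply does not remove the conflict. If the single item counts contacts, the Trial Outcomes section misnames a primary outcome. If it counts persons, the Statistical Analysis Plan misnames its dependent variable. If there are two items, the declared one is not the one modelled. Each case needs a correction. Persons against contacts is also a larger gap than implemented against adopted, because it changes what is counted.

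**Conclusion.** The concern holds as a conflict between sections over the unit of a primary outcome: persons are declared and summarised, and contacts, as worded, are modelled. Confidence is high that the sections conflict, and moderate that the modelled variable really differs from the declared one; the documents alone cannot settle the latter.

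If the variables differ, the size depends entirely on how unequal contacts per participant are between arms. Under the assumed shares of 50% and 25%, with at most one further contact each, no difference in people reached would appear as a ratio of 0.83 or 1.20. With equal shares there is no distortion. This is an illustration of scale and not an estimate of bias in this trial.

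This is more than a missing detail, because following the text literally yields a contact-based ratio where a person-based one was declared.

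**What to change.** Check the survey instrument for what was asked, then make the Trial Outcomes section and the Statistical Analysis Plan agree.

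- **If participants receiving naloxone were counted separately:** make that 3-month count the dependent variable of the second primary model, keep the stated offset, and report refill or training contacts as secondary. The result should be read as persons supplied per syringe-service contact. That rate can fall when visits per person rise, even if the same number of people are reached, so it should not be presented as a plain count of people.
- **If there is one item:** use one name and one definition in both sections, and report and interpret the result as what the item counts. If it counts contacts, do not describe the result as people reached.

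The cost is one model re-run in the first case and a wording correction in the second. Neither needs new data. If only contacts were collected, the further cost is interpretive: the trial could then report naloxone contacts but could not claim a result on the number of participants reached.

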#### Covariates

The baseline survey also collected information on region of operation, the number of staff and volunteers at the SSP, staff training in OEND, the prior year's annual budget in dollars, the number of participant contacts at the SSP in the past 3 months.

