#### Targeted Sample Size

The targeted sample size was estimated using PASS software [49]. We estimated that a sample of 100 SSPs (50 per arm) would provide 80% statistical power to detect a statistically significant ( $p<0.05$ ) medium effect size (Cohen's  $d = 0.45$ )[50] between study arms, assuming an

alpha of 0.05, standard deviation of 1.0 and two repeated measurements (baseline and 12-month follow-up) with a first-order autoregressive covariance structure and a correlation between observations on the same SSP of 0.3.

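### Both count models force mean naloxone output to be proportional to syringe-service contacts; if the true slope is below 1, precision is lost, and one baseline covariate guards against that

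*Combined protocol and SAP*

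**What the plan says.** The Statistical Analysis Plan states: "Negative binomial regression models were used to compare the number of naloxone doses distributed and contacts for naloxone refills or trainings by condition". It adds that "the number of contacts for syringe services in the past 3 months was included as an offset". The reason appears with the descriptive summaries: "Given the varying sizes of SSPs, counts of naloxone doses and individuals receiving naloxone were summarized as a rate per number of participant contacts".

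One further term is planned, in one model only: "The model for naloxone doses was adjusted for baseline rate given the difference between conditions at baseline". The other count model has no baseline term. Neither model has an estimated coefficient for contacts, another measure of program size, or a check of proportionality. The section does not say whether the offset uses baseline or 12-month contacts. The Covariates section shows that a size measure exists at baseline: "the number of participant contacts at the SSP in the past 3 months".

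The Trial Outcomes section says that "the primary outcomes were the number of naloxone doses distributed in the past 3 months; the number of SSP participants receiving naloxone in the past" three months, plus the number of best practices. The third outcome is compared by t-test and is not affected by this point.

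**The concern.** With an offset the model is log(mean) = a + d × arm + 1 × log(contacts), taking the offset on the log scale as usual. If the true slope is b, the residual carries (b − 1) × log(contacts). The plan scales by contacts because programs differ in size. A wrong fixed slope puts part of that size variation back as noise.

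There are two reasons to doubt a slope of 1:

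- **Units.** Contacts count repeat visits, while individuals receiving naloxone are people. Where contacts differ because visit frequency differs, people reached per contact falls as contacts rise.
- **Timing.** If the offset is baseline contacts, changes in program size over 12 months would tend to pull the slope below 1, even if counts follow current contacts exactly.

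At stake is precision in up to two of the three primary comparisons. The extra variation also need not follow the gamma form that the negative binomial assumes, so model-based standard errors can be too small.

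**Working it through.** **1. The plan's own figure.** The Targeted Sample Size section says: "We estimated that a sample of 100 SSPs (50 per arm) would provide 80% statistical power". Its inputs are d = 0.45, SD 1.0, two measurements, correlation 0.3 and alpha 0.05 (two-sided assumed).

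- Time-averaged variance: (1 + 0.3)/2 = 0.65, so SD = 0.806.
- n per arm = 2 × (1.960 + 0.842)² × 0.65 / 0.45² = 50.4, so 51. Power at 50 per arm is 0.797.

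The figure is reproduced. It describes a continuous repeated-measures comparison, not either count model, so 80% serves below only as a reference level.

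**2. Log-scale approximation.** Let t be the SD of log contacts and s the residual SD. Fixing the slope at 1 multiplies the variance of the effect by 1 + (1 − b)² × t² / s². The documents give none of b, t or s.

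- Example: b = 0.7, t = 1.2, s = 1.0 gives 1 + 0.09 × 1.44 = 1.13. Power falls from 0.80 to Φ(2.802/√1.13 − 1.960) = 0.75.
- Over t = 0.8 to 1.6 and s = 0.8 to 1.3, 80% power becomes 78–80% at b = 0.9, 67–79% at b = 0.7 and 51–76% at b = 0.5.

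**3. What visit frequency alone implies.** Two programs each reach 100 of 200 participants. At 3 visits a quarter the rate is 100/600 = 0.167; at 12 visits it is 100/2,400 = 0.042. Suppose people reached follow participant numbers, and visit frequency varies independently of them. Then b = 1 − Var(log frequency)/t².

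- If 3 to 12 visits spans ±2 SD, the variance is (ln 4 / 4)² = 0.12. Then b = 0.88 at t = 1.0 and 0.93 at t = 1.3.
- If it spans ±1 SD, the variance is (ln 4 / 2)² = 0.48. Then b = 0.52 and 0.72.

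**4. Negative binomial simulation.** Assumed: 50 per arm, dispersion 1.0, rate ratio 1.75, correlation 0.5 between the baseline and follow-up program effects, model-based standard errors, 2,500 trials per cell. Monte Carlo error is about 0.8 points. Power in %, fixed slope v free slope:

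| b | t | No baseline rate | Baseline rate (offset) v log rate (free) | Log baseline rate in both |
|---|---|---|---|---|
| 1 | 1.0 | 80.9 v 80.0 | 85.0 v 85.8 | 85.6 v 85.8 |
| 1 | 1.5 | 80.9 v 80.8 | 85.5 v 85.4 | 86.1 v 85.4 |
| 0.85 | 1.0 | 79.2 v 79.4 | 84.2 v 85.3 | 85.3 v 85.3 |
| 0.85 | 1.5 | 78.5 v 80.7 | 84.2 v 86.8 | 85.6 v 86.8 |
| 0.7 | 1.0 | 77.4 v 80.8 | 83.6 v 87.1 | 85.6 v 87.1 |
| 0.7 | 1.5 | 72.1 v 80.0 | 80.6 v 85.6 | 81.7 v 85.6 |
| 0.5 | 1.0 | 69.5 v 79.0 | 78.8 v 85.0 | 80.9 v 85.0 |
| 0.5 | 1.5 | 61.9 v 79.3 | 74.2 v 86.6 | 79.3 v 86.6 |

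Without the baseline rate the loss is about 0–2, 3–8 and 10–17 points at b = 0.85, 0.7 and 0.5. In the fourth column, closest to the doses model, it is about 1–3, 4–5 and 6–12. That column also changes the rate to its log. With the log rate on both sides, the loss is 0–1.2, 1.5–3.9 and 4.1–7.3.

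**5. Type I error.** Same set-up with rate ratio 1 and t = 1.5. Without the baseline rate, offset v free slope gave 0.077 v 0.058 at b = 0.7 and 0.132 v 0.066 at b = 0.5. In the doses-model form (offset plus rate v free slope plus log rate) it was 0.071 v 0.060 and 0.098 v 0.063. Robust standard errors brought the offset model without the rate to 0.058 and 0.076. Its power (rate ratio 1.75, t = 1.5) then fell to 66.7% and 50.1%, against 80.1% and 79.5% with a free slope.

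**6. Which wave the offset uses.** Assumed: 105 programs, rate ratio 1.5, counts following follow-up contacts, correlation 0.8 between baseline and follow-up log contacts, 400 runs per cell. With t = 1.3 and dispersion 0.5, power with a follow-up offset v log baseline contacts alone was 82% v 55% at slope 1 and 77% v 68% at slope 0.7. A further check (250 runs per cell) gave 84% v 52% and 76% v 65%. Adding log baseline contacts while keeping the offset lost 0–2 points at slope 1, gained 0–6 at slope 0.7 and gained 6–13 at slope 0.5.

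**The case against.** **The premise is not in the documents.** They give no slope, no spread of contacts and no dispersion. A reader might infer that larger programs give less naloxone per visit, and hence that the trial has lost power. The documents support neither step. If contacts differ mainly through participant numbers, the slope is near 1 and nothing is lost. This stands, and it makes the point conditional.

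**The units may match.** A reader might infer that both models divide people or doses by visits. The model sentence instead names naloxone refill or training contacts, which would be contacts over contacts. The descriptive sentence and the Trial Outcomes section name individuals. The units argument therefore applies to the second model only if individuals are its outcome, and that model's match to a primary outcome is itself unclear. This stands.

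**The doses model is partly protected.** Baseline rate carries the same dependence on size and recovers part of the loss. This stands. The recovery is incomplete at low slopes, and the other model has no such term.

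**Swapping the offset for baseline contacts can do harm.** Step 6 shows this if the offset is follow-up contacts, and it would also change the estimand from a rate per contact. This stands against replacing the offset outright. It does not count against adding the covariate. If the offset is already baseline contacts, the arm effect is a ratio of counts at equal baseline contacts whether the slope is fixed or free.

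**The type I error result is limited.** It needs slopes well below 1 and model-based standard errors, and the plan does not state the variance estimator. This stands.

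**Conclusion.** The point holds as a conditional weakness of functional form. Proportionality is imposed in both count models and left unchecked, and a slope below 1 would cost precision. The size rests wholly on assumed slope, spread and dispersion: negligible near slope 1, moderate at 0.7, substantial at 0.5. The full loss applies only to the model without baseline rate. The upper figures also depend on the residual distribution. With lognormal residuals (105 programs, rate ratio 1.5), the variance ratio of offset to free slope was 1.14–1.30 at slope 0.7 and 1.41–1.98 at slope 0.5.

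A reader might go further and conclude that the analysis is invalid or that the offset must be dropped. Neither follows. With contacts measured before randomization, a wrong slope costs precision and does not bias the ratio. With follow-up contacts, dropping the offset could cost more than the fault. The case for acting is the asymmetry: protection is nearly free, and the baseline value is already collected.

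**What to change.** - State which survey wave supplies the offset.
- Add log baseline contacts as a covariate with an estimated coefficient in both negative binomial models. If the offset is follow-up contacts, keep it. If it is baseline contacts, the addition is the same as replacing the offset with a free slope, because the coefficient estimates b − 1.
- Retain the baseline-rate term in the doses model.
- Report the present offset-only specification as a sensitivity analysis. The plan is written in the past tense, so if results have been seen, declare the change and show both models side by side.
- State the outcome of the second count model in the same terms as the Trial Outcomes section.

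The cost is one degree of freedom per model, a sentence or two in the plan, and about 0–2 power points if the slope is truly 1. No new data are needed.

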#### Data Collection

We carried out an interview-administered survey at SSPs baseline visit and at their 12-month follow-up after all facilitation-based activities had occurred. SSPs were paid a \$50 incentive for their time (~30 minutes) completing the baseline and the 12-month follow-up survey. In addition, the study coordinator tracked the number of sessions and the number of hours between external facilitators and SSP teams as part of a log of implementation activities. Follow-up to complete the 12-month follow-up survey ended in February 2022, marking the end of the trial approximately 12 months after the last SSP was enrolled.

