#### Masking

Masking the SSP organizations and their staff to the assigned implementation strategy condition was not possible. Aside from the external facilitators who delivered the implementation strategies, research staff were blinded to all condition assignments, including the statistician throughout all analyses.

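### Only one of three primary outcomes is adjusted for its baseline value, and the reason given is an observed arm difference; the other two lose some precision and stay exposed to chance imbalance

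*Combined protocol and SAP*

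**What the plan says.** The Trial Outcomes section names three primary outcomes. The first is a 3-month count of doses given out; the other two are "the number of SSP participants receiving naloxone in the past 3 months, and the number of OEND best practices implemented". The Statistical Analysis Plan section treats their baseline values in three ways:

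- **Doses:** negative binomial regression with an offset, plus a baseline term. "The model for naloxone doses was adjusted for baseline rate given the difference between conditions at baseline".
- **Second count outcome:** negative binomial regression in which "the number of contacts for syringe services in the past 3 months was included as an offset". No baseline outcome term is named.
- **Best practices:** "The mean number of best practices adopted were compared by condition using a two-sample t-test".

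Baseline information was available in principle: "We carried out an interview-administered survey at SSPs baseline visit and at their 12-month follow-up". The Targeted Sample Size section relies on it, counting baseline as one of two repeated measurements with "a correlation between observations on the same SSP of 0.3". The Masking section says that "research staff were blinded to all condition assignments, including the statistician throughout all analyses". No rule set in advance for choosing baseline covariates appears anywhere, and the Trial Design section describes simple randomisation with no stratification.

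**The concern.** An observed difference between arms is a poor criterion for adjustment. Under randomisation that difference is chance. Adjustment is worthwhile when baseline predicts the 12-month outcome, and it is worthwhile whether or not the arms look balanced. Tying it to observed imbalance has three consequences:

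- The two unadjusted outcomes give up whatever precision their baseline values would have bought. The offset accounts for programme size, not for how much naloxone activity a programme already had.
- Given a realised imbalance, an unadjusted estimate is shifted by the baseline-outcome correlation times that imbalance. Simple randomisation does nothing to limit it.
- Readers cannot tell whether the dose result depends on its adjustment, or the other two results on the lack of it.

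Blinding the statistician makes deliberate selection of a favourable model less likely, but it does not turn a data-triggered choice into a prespecified one.

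**Working it through.** **Inputs** (Targeted Sample Size section): 50 per arm, d = 0.45, SD 1.0, alpha 0.05, two measurements, correlation r = 0.3. Sidedness is not stated; two-sided is assumed. Correlations of 0.5 and 0.7 are assumptions used to show a range.

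**1. The plan's own figure.** Averaging two measurements multiplies the variance by (1 + r)/2 = 1.3/2 = 0.65. Then n per arm = 2 × 0.65 × (1.960 + 0.842)² / 0.45² = 50.4, and power at 50 per arm is 79.7% (normal) or 78.9% (t). This agrees with the plan's statement that "a sample of 100 SSPs (50 per arm) would provide 80% statistical power". The described analyses, however, compare the arms at 12 months and do not average in the baseline.

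**2. Best practices, t-test against ANCOVA.** The standard error without adjustment is √(2/50) = 0.20. Adjusting for baseline multiplies the variance by 1 − r². Power is from the noncentral t distribution.

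| Analysis | Variance factor | Noncentrality | Power |
|---|---|---|---|
| t-test | 1.00 | 0.45/0.20 = 2.25 | 60.6% |
| ANCOVA, r = 0.3 | 0.91 | 2.25/√0.91 = 2.36 | 64.6% |
| ANCOVA, r = 0.5 (assumed) | 0.75 | 2.25/√0.75 = 2.60 | 73.0% |
| ANCOVA, r = 0.7 (assumed) | 0.51 | 2.25/√0.51 = 3.15 | 87.7% |

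At r = 0.3 the number needed per arm for 80% power falls from 78 to 71 (normal approximation). With the 105 programmes in the trial (52 and 53 per arm), power goes from 62.7% to 66.8%.

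**3. Count model.** This was simulated as negative binomial with offset log(contacts) and covariate log((baseline count + 0.5)/contacts), a log rate ratio of 0.45 and 50 per arm (4,000 to 6,000 replicates). The dispersion of 1, median of 300 contacts, 0.5 events per contact and correlated gamma site effects are assumptions.

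| r | Power unadjusted | Power adjusted | Variance ratio |
|---|---|---|---|
| 0.3 | 62.0% | 63.8% | 0.966 |
| 0.5 (assumed) | 60.7% | 69.4% | 0.873 |
| 0.7 (assumed) | 62.1% | 79.3% | 0.694 |

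**4. Adjusting only when the arms differ.** The document gives no threshold, so triggers of baseline p < 0.05 and p < 0.10 are assumed. Normal outcomes, r = 0.3, 20,000 replicates:

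| Rule | Power | Type I error |
|---|---|---|
| Never adjust | 60.3% | 4.8% |
| Adjust if p < 0.05 | 60.4% | 4.6% |
| Adjust if p < 0.10 | 60.6% | 4.5% |
| Always adjust | 63.7% | 4.8% |

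A separate run of 40,000 replicates gave power of 60.2% (never), 60.4% (trigger p < 0.05) and 64.0% (always). The trigger rule recovers almost none of the gain and is slightly conservative.

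**5. Effect of a realised imbalance.** Given a baseline difference of z standard errors and no treatment effect, the unadjusted test statistic is approximately N(r × z, 1 − r²). At r = 0.3:

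| z | Imbalance | Shift in estimate | Conditional false-positive rate |
|---|---|---|---|
| 0 | 0 | 0 | 4.0% |
| 1 | 0.20 SD | 0.3 × 0.20 = 0.06 SD | 5.0% |
| 2 | 0.40 SD | 0.3 × 0.40 = 0.12 SD | 8.1% |

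Against the 0.45 target, these shifts are 0.06/0.45 = 13% and 0.12/0.45 = 27%.

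**The case against.** The strongest reply is that little is lost on the plan's own numbers. The only correlation given is 0.3, and it belongs to a generic outcome with SD 1.0. At that value adjustment gains about 4 power points for best practices and about 2 for the count model. The larger gains rest on assumed correlations. A one-standard-error imbalance leaves the conditional false-positive rate at 5.0%, and the document does not report how well the two unadjusted outcomes were balanced. All of this stands, and it limits how serious the point is.

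The same holds for several factual limits:

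- No section says that a best-practice count was taken at baseline; the Data Collection and Targeted Sample Size sections only imply it.
- If *adopted* means newly adopted, baseline status is already partly built into the outcome and the 9% variance figure does not apply.
- That the second count model is unadjusted is inferred from no baseline term being named, though this is the natural reading.
- The document discloses the reason for adjusting doses, and nothing shows that the choice was made after 12-month results were seen.
- The three outcomes use different models and scales, so uniform adjustment makes their handling consistent but not their effect sizes comparable.

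It could also be argued that adjustment inflates the size of the count test. One simulation gave type I error of 5.9% adjusted against 5.6% unadjusted at r = 0.3, and 6.0% against 5.2% at r = 0.7. A second found no difference at either correlation (5.3% in both models at r = 0.3; 6.2% and 6.3% at r = 0.7). Both models can run a little above 5% at this sample size, but the excess cannot be put down to the baseline term, so this objection does not stand.

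**Conclusion.** The concern holds. One of three primary outcomes is adjusted for baseline, the stated reason is an observed arm difference, and no advance rule is given. The harm is lost precision on the other two and, given a sizeable chance imbalance, a shifted estimate. It is not a raised overall false-positive rate: unadjusted tests keep about 5% and the trigger rule is slightly conservative.

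At r = 0.3 the loss is modest: 9% of variance for best practices and about 3% for the count model. It becomes substantial only if the true correlation is nearer 0.5 or 0.7, which the document does not establish. The best-practices figure assumes that a baseline count exists and that the outcome is the 12-month total; the count-model figures rest on the assumed dispersion and rates. Adjustment would not restore the planned 80% power at r = 0.3. It recovers about 4 of the roughly 18 points between 60.6% and 78.9%, and the rest of that gap is a separate matter. The change is worth making because it costs almost nothing and shows whether the conclusions depend on the choice.

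**What to change.** Report each primary outcome at 12 months adjusted for its own baseline value, whatever the observed balance.

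- **Count outcomes:** keep negative binomial regression with the offset and add the baseline rate in a form defined at zero, such as log((baseline count + 0.5)/baseline contacts). First reconcile the second outcome, which is a count of participants in the Trial Outcomes section but of refill or training contacts in the Statistical Analysis Plan section. The baseline variable must match the outcome modelled.
- **Best practices:** state whether the outcome is the 12-month total or newly adopted practices, since one section says *implemented* and the other *adopted*. Use ANCOVA on the baseline count if it was collected; if not, say so and keep the t-test.
- **Doses:** show the model without the baseline term as well, and state plainly that adjustment was chosen after the baseline difference was seen.
- **Labelling:** the document describes completed analyses, so mark the newly adjusted models as post hoc and place them beside the existing results without replacing them.

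The cost is up to two adjusted models, one unadjusted dose model, one degree of freedom per adjusted model and a few sentences. No new data are needed if the baseline best-practice count exists; otherwise that outcome stays unadjusted.
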